Clinical Development

AMG334/Erenumab/Aimovig®

AMG334A2401 / NCT03927144

A 12-month prospective, randomized, interventional, global, multi-center, active-controlled study comparing sustained benefit of two treatment paradigms (erenumab qm vs. oral prophylactics) in adult episodic migraine patients

Statistical Analysis Plan (SAP) Amendment

Author: Trial Statistician, [REDACTED]

Document type: SAP Documentation

Document status: Final Amendment 2

Release date: 25-Oct-2021

Number of pages: 51

Property of Novartis
For business use only

May not be used, divulged, published or otherwise disclosed
without the consent of Novartis

Document History – Changes compared to previous final version of SAP

Date	Time point	Reason for update	Outcome for update	Section and title impacted (Current)
07- May- 2019	Prior to DB lock	Creation of final version	N/A - First version	NA
01- Oct- 2021	Amendment 1	COVID-19 impact sensitivity analysis	Added analysis to study impact of randomization, study/treatment discontinuations, dose interruptions Added analysis to study impact on Protocol deviations Added analysis to study impact on demographics Added analysis to study impact on primary endpoint	Section 2.3.1 Section 2.3.2 Section 2.3.3 Section 2.5.4
	Visit mapping details		Updated details based on analysis visit instead of dose dates	Section 2.1.1.6
	Protocol amendment	PTA phase	Added details about PTA phase and endpoints collected during PTA	Section 1.1, 1.2
	Updated text to clarify randomized treatment		Updated text from “randomized treatment” to “initially assigned treatment”	Throughout the SAP
	Sensitivity analyses with corrected stratification factor		Added analysis by correcting strata for mis-stratified subjects	Section 2.5.5
	Analysis for COVID-19 and Hypertension AEs based on SMQ and for		Summary of treatment emergent AEs will be provided for COVID-19 and hypertension data by SMQ levels.	Section 2.8.1

Date	Time point	Reason for update	Outcome for update	Section and title impacted (Current)
		constipation based on CMQ	Summary of treatment emergent AEs will be provided for constipation by CMQ and corresponding preferred term.	
			Summary of exposure adjusted subject incidence rates for treatment emergent AEs and SAEs will be provided by primary system organ class and preferred terms.	Section 2.8.1

5.2	AEs coding/grading	42
5.3	Laboratory parameters derivations	43
5.4	Rule of exclusion criteria of analysis sets.....	43
5.5	Statistical models	43
5.5.1	Primary analysis	43
5.5.2	Secondary analysis	44
5.6	Important derivations.....	44
5.7	MMD derivation, exceptions	48
5.7.1	Assigning Headache and Migraine Days to Events Spanning Midnight.....	48
5.7.2	Spanning Midnight Rules for Multi-Day Events Longer Than Two Days.....	49
5.8	Patient Global Impression Change (PGIC).....	50
5.9	The Columbia-Suicide Severity Rating Scale (C-SSRS)	50
6	Reference	51

List of tables

Table 1-1	Objectives and related endpoints	10
Table 2-1	Study visit windows	14
Table 2-2	Study intervals for safety analysis.....	15
Table 2-3	Study intervals for efficacy endpoints – Erenumab and Oral prophylactics	19
Table 2-4	Summary of primary endpoint and analysis methods	27
Table 2-5	Summary of secondary efficacy endpoints and analysis methods	31
Table 2-6	Clinically Notable Laboratory Values	34
Table 2-7	ECG Abnormality Ranges.....	35
Table 2-8	Vital Signs Notable Criteria.....	35
Table 5-1	Imputation of AE/Concomitant dates.....	37
Table 5-2	Rules for handling missing and incomplete eDiary data	39
Table 5-3	Deviation Codes Description	43
Table 5-4	Patient classification.....	43

List of abbreviations

AE	Adverse event
ATC	Anatomical Therapeutic Classification
CSR	Clinical Study report
eCRF	Electronic Case Report Form
EOS	End of Study
FAS	Full Analysis Set
IAT	Initially assigned treatment
IP	Investigational Product
MedDRA	Medical Dictionary for Drug Regulatory Affairs
MMD	Monthly Migraine Days
NCI	National Cancer Institute
PD	Protocol Deviation
PK	Pharmacokinetics
PRO	Patient-reported Outcomes
PT	Preferred Term
PTA	Post Trial Access
qm	Monthly once
QoL	Quality of Life
SAP	Statistical Analysis Plan
SAF	Safety Set
SOC	System Organ Class
SoC	Standard of Care
TF	Treatment Failure
TFLs	Tables, Figures, Listings
WHO	World Health Organization

1 Introduction

This statistical analysis plan (SAP) describes all planned analyses for the Clinical Study Report (CSR) of study AMG334A2401, a 12-month phase IV, prospective, randomized, interventional, global, multi-center, active-controlled study comparing sustained benefit of two treatment paradigms (erenumab qm vs. oral prophylactics) in adult episodic migraine patients.

The content of this SAP is based on protocol AMG334A2401 version 02. This SAP includes analysis for core phase data. For extension phase, separate SAP will be developed.

Data will be analyzed by Novartis according to the data analysis section 12 of the study protocol. Important information is given in the following sections and details will be provided, as applicable, in [Appendix 16.1.9 of the CSR](#).

1.1 Study design

This study uses 2-treatment arm (AMG334 versus standard of care (SoC) oral prophylactic treatment), parallel group randomized (2:1 [AMG334 (70 mg or 140 mg) : SoC oral prophylactic]), open-label in adult patients with episodic migraine who have previously failed 1 or 2 prophylactic migraine treatments. The following periods are included in the study design, with study visits at 4-week intervals after completion of screening:

- Screening period (0-2 weeks): required for all subjects to assess initial eligibility and to obtain informed consent
- Baseline period (4 weeks) – All subjects successfully completing the screening period will be invited to participate. Eligibility for randomization will be assessed based on migraine frequency and diary compliance during this period. Randomization will be stratified by prior prophylactic migraine medication treatment failure (due to insufficient efficacy or poor tolerability) reported during screening / baseline period: 1 treatment failure (TF1) vs 2 treatment failures (TF2). A 30% cap of randomized subjects to the TF2 strata will be implemented. The stratification and 30% cap will be implemented within IRT.
- Open-Label Randomized Treatment Period (52 weeks): All subjects successfully completing the Baseline Period will be invited to participate. Eligible subjects will be randomized 2:1 to one of two treatment arms [AMG334 s.c. q.m. versus SoC oral prophylactic (active comparator)]. Only monotherapy will be allowed in both arms and no concomitant use of other prophylactics for migraine specifically should be used. At the end of this period, the final assessment to address the effect of AMG334 compared to oral prophylactic cycling on the net benefit and related objectives will occur. The last dose for AMG334 will occur at Week 48 (monthly dose) and the last dose for SoC will occur at Week 52.
 - Switching: Treatment (failure) status and decision on whether or not to switch to a new treatment will be checked at every visit and will be based on investigator and subject discretion (based on efficacy/tolerability/satisfaction but not based on prespecified cutoffs for certain parameters). In both arms, switching will be allowed within approved prophylactics in the respective country for prophylaxis of migraine. Subject randomized to AMG334 arm can

switch to oral prophylactics and subject randomized to oral prophylactics arm can switch to only other oral prophylactics and not to AMG334.

- Follow-Up Period (16 weeks) as per protocol version 0 and 1– A follow-up visit 16 weeks after the last dose of treatment (AMG334 or SoC oral prophylactic) will be required as part of routine safety monitoring. As per protocol amendment 2, subject may chose to enter extension phase or discontinue study. This means follow up data will not be available for all subjects.

Extension Phase (as per protocol amendment 2)

- Post-Trial Access Open-Label Treatment Period (52 weeks) - Patients completing visits through week 52 of the Core Phase will be eligible to participate. Patient eligibility will be determined by the investigators opinion as follows: 1) patients treated with erenumab must have benefited from erenumab treatment and 2) patients on Standard of Care (SoC) oral prophylactic must be in need of a treatment switch. PTA to erenumab will be provided for up to 52 weeks (based on continued benefit of erenumab treatment) in all eligible patients; this will ensure erenumab access until country-level launch and subsequent reimbursement decision in all countries. Should a treatment gap exist between the Core and Extension Phase due to a delay of HA/EC approvals or other administrative/logistical reasons, the subject may enter the Extension Phase at a later time. During this treatment gap, the patient would remain in the main study and is allowed to be treated with any medication as deemed appropriate by the investigator to manage the patient's migraines. Upon HA and EC approval of the Extension Phase, the patient will then be administered study drug corresponding to the Week 52 dose and will continue dosing every 4 weeks as per protocol. Patients will be required to follow all protocol requirements for treatments allowed and for prohibited medications ([Protocol Section 6.2.2](#))

End of Trial will occur when the last subject completes their last visit (LPLV) of the study. The primary analysis will occur when the last patient completes the Core Phase, prior to the start of the Extension Phase. The main study report will be prepared and finalized at this time for all data from the Core Phase. An additional study report will be prepared for the Extension Phase after all patients have completed their respective last visit (LPLV) of the Extension Phase and will report data for the Extension Phase.

Approximately 591 subjects will be enrolled into the trial.

There is no planned interim analysis for this study.

Note:

- Treatment discontinuation does not imply study discontinuation. Every effort should be attempted to ensure subjects complete the study visits event if treatment is discontinued. After study completion, post-trial access to AMG334 will be offered to the study participants as needed.
- Some eligibility criteria will be checked at screening visit and some at baseline.
- Treatment disposition form will be filled for the last drug taken by the subject regardless of switching and not only for initially assigned treatment.

[figure not shown]
- There can be gap between end of first treatment and start of switched treatment.

[figure not shown]
1.2 Study objectives and endpoints

In the table below and throughout this SAP Month 6 is equivalent to Week 24, and Month 12 is equivalent to Week 52. Also, all analysis is planned for initially assigned treatment where initially assigned treatment is refers to randomized treatment.

Table 1-1 Objectives and related endpoints

Objective(s)	Endpoint(s)
Primary objective(s)	Endpoint(s) for primary objective(s)

• To demonstrate the superiority of subcutaenous erenumab compared to oral prophylactic(s) on sustained benefit defined as % subjects completing one-year on the initially assigned treatment and achieving at least a 50% reduction from baseline in monthly migraine days at month 12.	
• Proportion of subjects who complete initially assigned treatment and achieve at least 50% reduction from baseline in monthly migraine days at Month 12
Secondary objective(s)	Endpoint(s) for secondary objective(s)

• To evaluate the effect of erenumab compared to oral prophylactic(s) on overall subject retention defined as % subjects completing study on the initially assigned treatment• To evaluate the effect of erenumab compared to oral prophylactic(s) on the change from baseline in monthly migraine days during the treatment period• To evaluate the effect of erenumab compared to oral prophylactic(s) on the subject's assessment of the change in clinical status since the start of treatment as measured by the Patients' Global Impression of Change (PGIC) Scale	
• Proportion of subjects completing the study at Month 12 on the initially assigned treatment• Cumulative average change from baseline on the monthly migraine days during the treatment period for the subjects on initially assigned treatment (Months 1-12)• Proportion of responders (PGI-I score ≥ 5) as measured by PGIC at month 12 for subjects completing the treatment period at Month 12 on initially assigned treatment

2 Statistical methods

2.1 Data analysis general information

The final analysis will be performed by Novartis or a designated CRO. The current version of SAS or R software or later available versions will be used to perform all data analyses and to generate tables, figures and listings.

Data included in the analysis

The analysis cut-off date for the primary analysis of study data will be established after last subject completes or discontinues core phase that is when all subjects either complete week 52 on core phase or complete FU or discontinue early prior to week 52. All statistical analyses will be performed using all data collected in the database up to the data cutoff date. All data with an assessment date or event start date (e.g. vital sign assessment date or start date of an adverse event) prior to or on the cut-off date will be included in the analysis. Any data collected beyond the cut-off date will not be included in the analysis and will not be used for any derivations.

All events with start date before or on the cut-off date and end date after the cut-off date will be reported as ‘continuing at the cut-off date’. The same rule will be applied to events starting before or on the cut-off date and not having documented end date. This approach applies, in particular, to adverse event and concomitant medication reports. For these events, the end date will not be imputed and therefore will not appear in the listings.

General analysis conventions

Pooling of center: Unless specified otherwise, data from all study centers will be pooled for the analysis. Due to expected small size of centers, no center effect will be assessed.

Qualitative data (e.g., gender, race, etc.) will be summarized by means of contingency tables by treatment group; a missing category will be included as applicable. Percentages will be calculated using the number of subjects in the relevant population or subgroup as the denominator.

Quantitative data (e.g., age, body weight, etc.) will be summarized by appropriate descriptive statistics (i.e. mean, standard deviation, median, minimum, and maximum) by treatment group.

2.1.1 General definitions

2.1.1.1 Study treatment

Subjects will be randomized to one of the following treatment groups:

- Erenumab labelled as AMG334 (70mg or 140mg): pre-filled 1mL syringes (PFS) containing 70mg/1mL of AMG334. Note: if and when 140mg/1mL PFS become available, the dose may be administered by a single injection.
- Comparator: locally approved oral prophylactic migraine medication.

For this trial, study treatment refers to AMG334 or oral prophylactics as assigned to a subject at randomization.

Unless otherwise specified, analysis will be presented by initially assigned treatment i.e. randomized treatment.

2.1.1.2 Study dates

• Date of first administration study treatment

The date of first administration of study treatment is derived as the date on which a subject is administered the first nonzero dose of study treatment following randomization, which may be the same day or after the randomization date. For subjects who are randomized but not dosed with study treatment after randomization, date of first administration of study treatment is considered missing.

• Date of last administration of study treatment

The date of last administration of study treatment is defined as the last date when a nonzero dose of study treatment was administered.

2.1.1.3 Study day

Study Day 1 is defined as the first dose date of study treatment during initially assigned treatment period. For subjects who are randomized but not dosed after randomization, the Study Day 1 is defined as the date of randomization. Also, for subjects who are randomized but not dosed during initially assigned treatment period and received dose in switched period, the Study Day 1 is defined as the date of randomization.

Study Day is defined as the number of days from Study Day 1.

- Before Study Day 1:

Study Day = (Date of Interest – Date of Study Day 1)

- On or after Study Day 1:

Study Day = (Date of Interest – Date of Study Day 1) + 1

Therefore the day prior to Study Day 1 is -1.

The study day will be displayed in the data listings.

2.1.1.4 Baseline

The baseline period for efficacy analysis is defined as the period between week -4 visit (when eDiary device is dispensed to the subject for daily data capture) and the day prior to study day 1 (study day 1 is not included).

A baseline for subject reported outcome (PRO) and safety (including Columbia-Suicide Severity Rating Scale (C-SSRS)) values refers to the last evaluable measurement prior to the first administration of the study drug, irrespective of re-screening. In this case, baseline values will be the value obtained on the day of the randomization (Day 1, Visit 101), or on an earlier visit (scheduled or unscheduled) which is the closest to Visit 101, if Visit 101 is missing or the assessment was not done at baseline.

Baseline weight and height are taken from vital signs screening visit.

eCSSRS is collected at screening or before randomisation and patients should complete “lifetime assessment eCSSRS questionnaire” at screening and if need arises during the course of the trial complete “since last contact eCSSRS questionnaire”. Hence, we do not have “Evaluation timeframe” (TMFRM) variable collected and baseline eCSSRS will correspond to the last evaluable measurement prior to the first administration of the study drug, irrespective of re-screening. For this analysis, each subject can only be counted once for each event. However, a subject can be counted in several different events.

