6.1.3 Treatment arms/group

At the start of the Open-Label Randomized Treatment Period (Day 1) subjects will be assigned to either erenumab (70 mg or 140 mg) or SoC oral prophylactic at the Treatment Visit in a 2:1 ratio, stratified by prior prophylactic migraine medication treatment failure (1 or 2 treatment failures due to efficacy or tolerability, with cap of 30% on 2 treatment failures) reported during the Screening/Baseline Period. In the erenumab arm, subjects may be treated with either 70 mg or 140 mg based on the investigator's assessment. This information and reason for dose selection should be documented in the source and eCRF. Erenumab and SoC oral prophylactics must be used in accordance with the locally approved product label/package insert.

Study medication will be:

- Erenumab (labelled as AMG334): pre-filled 1mL syringes (PFS) containing 70 mg/1mL of erenumab.

- Comparator: locally approved oral prophylactic migraine medication.

Eligible subjects that complete the Core Phase (see [Section 3.0](#) for eligibility details) will be allowed to enter the Extension Phase and receive erenumab (70 mg or 140 mg).

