6.3.2 Treatment assignment, randomization

At Treatment Visit (Day 1 of Core Phase), all eligible subjects will be randomized via Interactive Response Technology (IRT) to one of the treatment arms. The investigator or his/her delegate will contact the IRT after confirming that the subject fulfills all the inclusion/exclusion

criteria. The IRT will assign a randomization number to the subject, which will be used to link the subject to a treatment arm and will specify a unique medication number for the first package of study treatment to be dispensed to the subject.

The randomization numbers will be generated using the following procedure to ensure that treatment assignment is unbiased and concealed from subjects and investigator staff. A subject randomization list will be produced by the IRT provider using a validated system that automates the random assignment of subject numbers to randomization numbers. These randomization numbers are linked to the different treatment arms, which in turn are linked to medication numbers. A separate medication list will be produced by or under the responsibility of Novartis Global Clinical Supply using a validated system that automates the random assignment of medication numbers to packs containing the study treatment.

Randomization will be stratified by prior prophylactic migraine medication treatment failure (1 or 2 treatment failures due to efficacy or tolerability) reported during Screening/Baseline Period. The IRT will cap the randomization to the "2 prior treatment failure" strata to 30%.

The randomization scheme for subjects will be reviewed and approved by a member of the Randomization Office.

Patients that complete the Core Phase will be allowed to enter a 52 week Extension Phase (see [Section 3.0](#) for details).

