6.7.1 Handling of study treatment and additional treatment

6.7.1.1 Handling of study treatment

Erenumab must be received by a designated person at the study site, handled and stored safely and properly and kept in a secured location to which only the investigator and designated site personnel have access. During the Extension Phase erenumab may be provided to the patient at the quarterly visits if the patient opts to self-administer study medication at home. For patients opting to self-administer study medication at home documented training on the proper storage procedures is required. SoC oral prophylactics will be sourced locally and will be reimbursed by the Sponsor. Upon receipt, all study treatment must be stored according to the instructions specified on the labels and in the prescribing information/package insert. Clinical supplies are to be dispensed only in accordance with the protocol. Technical complaints are to be reported to the respective Novartis Country Pharma Organization (CPO) Quality Assurance.

Medication labels will be in the local language and comply with the legal requirements of each country. They will include storage conditions for the study treatment but no information about the subject except for the medication number.

The investigator must maintain an accurate record of the shipment and dispensing of study treatment in a drug accountability log. Monitoring of drug accountability will be performed by monitors during site visits or remotely and at the completion of the trial. Subjects will be asked to return all unused study treatment and packaging at the end of the study or at the time of discontinuation of study treatment.

At the conclusion of the study, and as appropriate during the course of the study, the investigator will return all unused study treatment, packaging, drug labels, and a copy of the completed drug accountability log to the Novartis monitor or to the Sponsor address provided in the investigator folder at each site.

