Baseline period	Baseline	From ediary device assignment date (or week -4 visit)	Day prior to study day 1
Treatment Period	Week 4	Study day 1	
• Week 4 visit date - 1• Study day 1 + 27 days if Week 4 visit is missed 
Note: if day 1 dose is the last dose subject received, the rest of monthly rates during treatment period will be calculated based on consecutive 28-day interval beginning

	Week 8	
• Week 4 visit date• Week 4 analysis visit end date + 1 day if Week 4 visit is missed	
• Week 8 visit date – 1• Week 4 analysis visit start date + 27 days if Week 8 visit is missed
	Week 12	
• Week 8 visit date• Week 8 analysis visit end date + 1 day if Week 8 visit is missed	
• Week 12 visit date – 1• Week 12 analysis visit start date + 27 days if Week 12 visit is missed
	Week 16	
• Week 12 visit date	
• Week 16 visit date – 1

		
 • Week 12 analysis visit end date + 1 day if Week 12 visit is missed 	
 • Week 16 analysis visit start date + 27 days if Week 16 visit is missed
	Week 20	
 • Week 16 visit date • Week 16 analysis visit end date + 1 day if Week 16 visit is missed 	
 • Week 20 visit date – 1 • Week 20 analysis visit start date + 27 days if Week 20 visit is missed
	Week 24	
 • Week 20 visit date • Week 20 analysis visit end date + 1 day if Week 20 visit is missed 	
 • Week 24 visit date – 1 • Week 24 analysis visit start date + 27 days if Week 24 visit is missed
	Week 28	
 • Week 24 visit date • Week 24 analysis visit end date + 1 day if Week 24 visit is missed 	
 • Week 28 visit date – 1 • Week 28 analysis visit start date + 27 days if Week 28 visit is missed
	Week 32	
 • Week 28 visit date • Week 28 analysis visit end date + 1 day if Week 28 visit is missed 	
 • Week 32 visit date – 1 • Week 32 analysis visit start date + 27 days if Week 32 visit is missed

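### The SAP ends the efficacy baseline before first dose rather than before randomisation, so open-label days after allocation enter it for any subject who starts treatment late

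*SAP*

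**What the plan says.** Three SAP definitions combine.

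- Section 2.1.1.4 ends the efficacy baseline on "the day prior to study day 1 (study day 1 is not included". The baseline row of Table 2-3, in section 2.1.1.6, repeats the rule: "Day prior to study day 1".
- Section 2.1.1.3: "Study Day 1 is defined as the first dose date of study treatment during initially assigned treatment period". There is a second anchor: "For subjects who are randomized but not dosed after randomization, the Study Day 1 is defined as the date of randomization".
- Section 2.1.1.2 says of the first administration that it is a date "which may be the same day or after the randomization date". No upper limit on the gap is given.

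The protocol counts differently. Table 8-1 places the Baseline Period at Days -28 to -1, and section 6.1.3 makes Day 1 the day of allocation: "At the start of the Open-Label Randomized Treatment Period (Day 1) subjects will be assigned". The 4 to 14 migraine-day criterion is confirmed from the eDiary at that visit (sections 5.1 and 8.5.1).

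On supply, study staff inject erenumab at Core Phase visits (protocol 6.6.1), whereas "SoC oral prophylactics will be sourced locally and will be reimbursed by the Sponsor" (protocol 6.7.1.1). Section 6.4 makes treatment open to subjects and staff.

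**The concern.** A baseline should be closed before anyone knows the allocation. Under the SAP's rule it stays open until the first dose. If a subject is randomised on one day and starts treatment a week later, that week of diary entries counts as baseline although the subject already knows which arm it is.

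Baseline MMD has two uses that matter: it is the denominator of the 50% reduction in the primary endpoint (SAP 2.5.1 and 5.6), and it is a covariate in the mixed model for the secondary MMD endpoint (SAP 2.7.2). If knowing the allocation changes how headaches are experienced or recorded, the responder threshold moves with it. A late starter's analysis baseline can also differ from the one that made the subject eligible.

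The problem would be sharper if late starts fell mostly in one arm. An injection given at the visit leaves little room for delay. A locally sourced oral drug leaves more.

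**Working it through.** **The plan's own figure.** The only related figure is the sample size. Inputs from protocol 12.8.1: control rate 0.18, odds ratio 2, two-sided 0.05, 90% power, 2:1 allocation.

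- Erenumab rate = 2 × (0.18/0.82) / (1 + 2 × (0.18/0.82)) = 0.305, a difference of 12.5 points (the plan states 12%).
- The two-proportion formula with continuity correction gives 198 + 396 = 594, against 591 in the plan. Power of the Cochran-Mantel-Haenszel test at 394/197, with 70/30 strata and equal rates across strata, is 89.9% to 91.7% depending on the variance form.

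The 591 reproduces and does not depend on the baseline rule.

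**Share of baseline recorded after allocation.** For a delay of d days on a 28-day baseline the share is d/(28 + d). Delays are assumed, since none is given.

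- 3 days: 3/31 = 9.7%
- 7 days: 7/35 = 20%
- 14 days: 14/42 = 33%

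With the baseline closed before randomisation, the share is 0% for everyone.

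**Shift in one subject's baseline.** Assume 8 migraine days per 28 before allocation and a rate m times that afterwards. Prorated baseline = 28 × (8 + (8/28) × d × m)/(28 + d). For m from 0.7 to 1.3:

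- 3 days: 7.77 to 8.23 (about ±3%)
- 7 days: 7.52 to 8.48 (±6%)
- 14 days: 7.20 to 8.80 (±10%)

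**Effect on the 50% criterion.** This is a simulation, and all its inputs are assumptions. Individual rates are gamma with mean 8 per 28 days, and the 28-day baseline is screened to 4 to 14. The month-12 rate is 0.75 of the subject's own rate with lognormal noise (SD 0.4), so about 31% meet the criterion. The table shows the change in percentage points if every subject in an arm starts late, which is the effect per late starter.

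| Delay | m = 0.7 | m = 1 | m = 1.3 |
|---|---|---|---|
| 3 days | -4.4 | -3.2 | -1.9 |
| 7 days | -5.0 | -2.3 | +0.3 |
| 14 days | -6.2 | -1.7 | +2.9 |

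With 25% to 50% of the arm late, the range is -3.1 to +1.4 points.

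**What the unchanged-rate column means.** At m = 1 the shift is largest for the shortest delay, which is the wrong pattern for contamination. It largely reflects whole-number counts over exactly 28 days, which often put month 12 at exactly half of baseline; proration over a longer period breaks those ties. The SAP already breaks many of them in both arms: it allows baselines over 28 days and requires 80% diary compliance (5.6), and it prorates without rounding (5.1.4.1). With baselines of 28 to 33 days and 10% missing diary days (assumed), the m = 1 shift falls to about -0.4 to -1.1 points per late starter.

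**Scaling to net benefit.** Only subjects who stay on assigned treatment can change status. Assume 50% retention, unrelated to late start.

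- Unchanged reporting: from 0.4 × 0.25 × 0.5 = 0.05 to 1.1 × 0.5 × 0.5 = 0.28 points lower in that arm.
- Reporting changed by up to 30% either way: -3.1 × 0.5 = -1.6 to +1.4 × 0.5 = +0.7 points. This range still includes the tie effect.

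The planned difference is 12 points.

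**The case against.** The best defence is that the rule is a recognised convention. Closing the baseline at first dose keeps every untreated day in it and no treated day, and it matches the SAP's PRO and safety baselines, which also use the last value before first drug. Table 8-1 puts randomisation and drug administration at the same Day 1 visit in both arms. If that schedule is followed, the SAP and protocol baselines coincide and nothing is contradicted. Section 2.1.1.2 is a date-derivation rule and names no arm. Local sourcing concerns supply and reimbursement; it does not say that oral subjects start later.

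Most of this stands. A reader might infer that baseline is measured differently in the two arms, or that open-label reporting drives responder status in the oral arm. The documents support neither as fact: they give no delays, by arm or overall, and no information on how reporting changes after allocation. Nor can a direction be claimed, since the sign above changes with the assumed reporting rate.

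What the defence does not answer is that the SAP expressly foresees a first dose after randomisation, sets no limit on the gap, and counts those open-label days as baseline. The convention is harmless when treatment is masked during the gap. Here it is not. The second anchor, for subjects never dosed on assigned treatment, does not affect the primary result because those subjects are non-responders in any case.

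**Conclusion.** The point holds as a minor weakness of definition. For any late starter, the SAP puts days with known allocation into the primary endpoint's denominator, and that baseline no longer matches the one used for eligibility. This follows from the text alone.

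Everything beyond that is conditional. That delays cluster in the oral arm is a plausible inference from how the drugs are given and supplied. The effect on net benefit depends on the share of late starters, the length of delay, retention and reporting behaviour, all unknown. On the assumptions shown, it is a fraction of a point if reporting is unchanged and at most about 1.6 points in the affected arm otherwise, against a planned 12. It is probably small and of unknown sign. It does not call the sample size or the primary test into question. The case for changing it is that a pre-allocation baseline removes the possibility at almost no cost.

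**What to change.** In SAP 2.1.1.4 and in the baseline row of Table 2-3, end the efficacy baseline on the day before randomisation for all FAS subjects. Both places must change, or the SAP will contradict itself.

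State that diary days from randomisation up to the day before first dose count in neither baseline nor the Week 4 interval. Table 2-3 starts that interval at Study Day 1, so those days would otherwise be left without a rule. The definition of Study Day 1 can stay as it is.

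Report the time from randomisation to first dose by arm. If the present rule is kept, add a sensitivity analysis of the primary endpoint with the randomisation-anchored baseline.

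The cost is a sentence or two, one table cell and one summary table. No new data are needed, and the 80% baseline compliance required for randomisation (23 of 28 diaries, SAP 5.6) already exceeds the 14-day minimum for proration. The downside is that a few untreated diary days are dropped for late starters.
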